6.14 Contraception

6.14.1 Contraception in Females

Women of childbearing potential, defined as all women physiologically capable of becoming pregnant, may be included in the study provided they are using highly effective methods of contraception during dosing and for 6 months after the last dose of IMCnyeso.

Highly effective contraception methods include the following:

- Total abstinence from sexual relations for the duration of the treatment when applicable to the lifestyle of the patient. Periodic abstinence (eg, calendar, ovulation, symptothermal and post-ovulation methods) and withdrawal are not acceptable methods of contraception.
- Female sterilization (surgical bilateral oophorectomy with or without hysterectomy) or tubal ligation at least 6 weeks before taking study treatment. In case of oophorectomy alone, this applies only when the reproductive status of the woman has been confirmed by follow-up hormone level assessment.
- Male sterilization (at least 6 months prior to Screening). For female patients on the study the vasectomized male partner should be the sole partner for that patient.
- Use of oral, injected, implanted, intravaginal, or transdermal hormonal methods of contraception (either estrogen and progestogen containing or progestogen-only) associated with inhibition of ovulation that have comparable efficacy (failure rate $< 1\%$), for example hormone vaginal ring or transdermal hormone contraception.

- Placement of an intrauterine device (IUD) or intrauterine system (IUS).

When using oral contraception, women should have been stable and on the same oral contraceptive pill for a minimum of 3 months before the start of study treatment.

Women are considered post-menopausal and not of childbearing potential if they have had 12 months of natural (spontaneous) amenorrhea with an appropriate clinical profile (eg, age appropriate and history of vasomotor symptoms), or have had surgical bilateral oophorectomy (with or without hysterectomy) or have had tubal ligation at least 6 weeks prior to study treatment. In the case of oophorectomy alone, only when the reproductive status of the woman has been confirmed by follow-up hormone level assessment is she considered not of childbearing potential.

6.14.2 Contraception in Males

Male patients must be surgically sterile or agree to use double barrier contraception from Screening to 6 months after the last dose of IMCnyeso.

6.15 Management of Adverse Reactions

Guidelines for management of AEs and dose modifications are presented in Table 6-4.

Grading of CRS is based on the American Society for Transplantation and Cellular Therapy (ASTCT) 2019 consensus grading system shown in [Section 13.1](#). All other AE are graded per NCI CTCAE v4.03.

Appropriate clinical experts should be consulted as deemed necessary in the judgement of the Principal Investigator for any AEs observed during the trial.

6.15.1 IMCnyeso Dose Reductions

Recommended dose reductions of IMCnyeso for observed toxicity should be as follows:

- All dose modifications should be based on the worst preceding toxicity
- The dose will be reduced ≥ 1 dose level from the initial prescribed dose for any toxicity requiring dose reduction, as per toxicity management guidelines. **NOTE:** Following a single dose-reduction, if there is no recurrence of toxicity with subsequent doses of IMCnyeso, return to the initial prescribed dose is permitted following discussion with the Sponsor Medical Monitor
- If toxicity recurs, the dose may be reduced again, by an additional ≥ 1 dose level

- Patients who require more than 2 dose reductions of IMCnyeso should permanently discontinue treatment

6.15.2 IMCnyeso Dose Interruptions

One to two doses of IMCnyeso may be omitted to permit resolution of treatment-related toxicity. If a patient who misses more than 2 consecutive doses due to a treatment-related toxicity is experiencing clinical benefit, and in the opinion of the Investigator, the benefit/risk profile favors continued treatment, then treatment may be restarted after discussion with the Sponsor Medical Monitor. If more than 3 consecutive doses of IMCnyeso are not administered due to treatment-related toxicity or if a > 21-day treatment interruption occurs, the default position is that the patient must then permanently discontinue study treatment.

Patients whose treatment is interrupted or permanently discontinued due to an AE or clinically significant laboratory value must be followed up at least once a week (or more frequently if clinically indicated) for 4 weeks, and at approximately 4-week intervals thereafter, until resolution or stabilization of the event, whichever occurs first.

Table 6-4: Recommended Management and Dose Modifications by Toxicity Grade and Type

Grade	Recommended Toxicity Management	Dose Modifications
Cytokine Release Syndrome (occurring at least 1 hour after the start of infusion) - refer to modified grading system in Table 13-1		
Grade 1	
If not already hospitalized, admit for close observation (eg, monitor vital signs hourly); implement supportive care per institutional standards. Provide anti-pyretics and analgesics as needed; monitor fluid balance (IV fluid support as indicated). Consider prophylactic electrolyte supplementation for patients receiving IV fluids with low-normal serum phosphorus or magnesium.
 
Serum should be collected for central lab cytokine assessments (see Section 7.4.6.4).
	May continue dosing.
Grade 2	
Notify the Sponsor within 24 hours of onset.
 
As above for Grade 1; additionally, monitor with continuous cardiac telemetry and pulse oximetry and follow organ function closely.
 
If the patient experiences dyspnea, consider supportive measures such as supplemental oxygen.
 
If the patient experiences hypotension, consider bolus IV fluids at a rate of approximately 1 L crystalloid per hour. If the patient is asymptomatic and non-orthostatic after infusion of 2 to 3 L administered over 2 to 3 hours, consider transition to maintenance IV fluids until resolved. If hypotension does not respond to fluids, consider systemic corticosteroids (eg, methylprednisolone 1 mg/kg IV twice daily).
	
Do not administer next scheduled dose of IMCnyeso until CRS has resolved.
 
 Overnight hospitalization is required for the scheduled next dose of IMCnyeso

Grade	Recommended Toxicity Management	Dose Modifications
Grade 3	
As above for Grade 2; additionally, systemic treatment with immunosuppressive agents (eg, methylprednisolone 2 mg/kg/day or equivalent and/or tocilizumab 8 mg/kg IV, not to exceed 800 mg/infusion) per institutional guidelines must be administered. Escalate level of care (eg, intensive care unit) as indicated.
 
For persistent hypotension, treat with a single vasopressor (with or without vasopressin).
 
For hypoxia, provide oxygen with a high-flow device.
	
Do not administer next scheduled dose of IMCnyeso until CRS has resolved.
 
 • Treatment may continue provided all the following conditions are met: 
 ○ Overnight hospitalization is required for the next scheduled dose of IMCnyeso ○ Reduce the IMCnyeso dose by \geq 1 dose level ○ Consider pre-medication (eg, methylprednisolone 1 mg/kg IV) $<$ 60 min prior to the start of the next scheduled infusion ○ If the patient experiences \leq Grade 1 CRS following the first reduced dose, then the next dose of IMCnyeso should be administered at the reduced dose without pre-medication, but must be hospitalized overnight for observation • Any patient that experiences recurrence of Grade 3 CRS following re-treatment should permanently discontinue study treatment unless the Investigator believes the overall benefit-risk favors continued treatment and following discussion and agreement with the Sponsor Medical Monitor
Grade 4	
As above for Grade 3; additionally, consider treating hypotension with multiple vasopressors, for hypoxia provide oxygen using a positive-pressure device, and consider other immunosuppressive agents for persistent or recurrent signs and/or symptoms as indicated (eg, infliximab or mycophenolate mofetil).
	
Study medication must be permanently discontinued.

Grade	Recommended Toxicity Management	Dose Modifications
Rash and/or Pruritus		
Grade 1	If symptomatic, consider the systemic antihistamine regimen (see Grade 2 guidance below).	May continue dosing.
Grade 2	
Treat according to institutional practice and/or implement guidance below. Use systemic management and/or local skin management as indicated by symptoms. With bullous formation or blistering rashes, consider dermatology consultation to rule out other causes (eg, bullous pemphigoid). Oral or topical corticosteroids can be used. If bullous formation or blistering recur, consult Sponsor Medical Monitor for guidance.
 
Systemic antihistamine (anti-pruritic) regimens: Recommended as first-line management of pruritus. Use non-sedating, long-acting antihistamines (cetirizine, 10 mg oral or equivalent). If a sedating antihistamine is preferred (eg, evening dosing) consider diphenhydramine 25 mg oral or IV. The use of sedating antihistamines should be minimized in patients with co-morbid pulmonary pathology including pulmonary metastases or underlying inflammatory airway disease such as COPD or asthma.
 
Topical corticosteroid regimens: When involved areas include face and/or intertriginous areas (including genitalia) recommend a low potency corticosteroid or antihistamine creams. For other body areas (ie, trunk and extremities), recommend a low to medium potency corticosteroid cream. Consider spray preparation for ease of application on trunk.
	May continue dosing.

Grade	Recommended Toxicity Management	Dose Modifications
Grade 3	
As above for Grade 2; additionally, oral corticosteroids can be considered in cases of symptomatic rash that do not respond to systemic antihistamine and topical corticosteroids.
 
Prednisolone 20-40 mg/day (or equivalent) should be given for as short a duration as clinically feasible to facilitate symptom resolution while minimizing any potential detrimental effect on efficacy.
 
In addition, montelukast 10 mg by mouth can be given to patients with pruritus refractory to antihistamine and local corticosteroid treatments. Patients with persistent, severe symptoms who fail to respond to the addition of montelukast can be treated with a single hydrocortisone 50 mg IV or prednisone 20 mg by mouth after discussion with the Sponsor Medical Monitor.
 
Consider performing a skin punch biopsy (see Section 7.4.6.3).
	
Do not administer IMCnyeso until rash / pruritus has improved to \leq Grade 1.
 
 • If Grade 3 rash / pruritus resolves to \leq Grade 1 in < 7 days, treatment may continue at same dose level. • If Grade 3 rash / pruritus resolves to \leq Grade 1 in 7–21 days, restart with \geq 1 dose-level reduction in IMCnyeso. • If the Grade 3 rash / pruritus does not resolve within 21 days, study medication must be permanently discontinued.
Grade 4	As above for Grade 3; additionally, consultation with a dermatologist is recommended.	Study medication must be permanently discontinued.
Infusion-related Reactions (occurring within 1 hour of starting the infusion) / Anaphylaxis		
All grades	Acute allergic reactions should be treated as needed using institutional guidelines. In the event of anaphylactic / anaphylactoid reactions, any therapy needed to restore normal cardiopulmonary status should be implemented immediately.	
Grade 1	Monitor vital signs at least approximately every 15 minutes through EOI.	May continue the infusion

Grade	Recommended Toxicity Management	Dose Modifications
Grade 2	
Treat according to institutional practice. Provide all supportive measures as indicated. Provide supplemental oxygen and fluids, as needed.
 
Monitor vital signs (eg, blood pressure, pulse, and temperature), pulse oximetry, and continuous cardiac telemetry (if clinically indicated) until resolution. Administer medications, supplemental oxygen, and/or IV fluids for symptomatic relief as needed. Antihistamines, acetaminophen (paracetamol), bronchodilator therapy, or corticosteroids (eg, methylprednisolone 1 mg/kg IV or equivalent) may be administered as needed, at the discretion of the Investigator.
	
Stop infusion and keep IV line open.
 
 • If a Grade 2 IRR resolves within 4 hours of onset with medical management, may restart the infusion provided all the following conditions are met: 
 ○ Oral pre-medications (eg, 1000 mg of acetaminophen [paracetamol], 50–100 mg diphenhydramine hydrochloride or alternative antihistamine) are administered within 60 minutes prior to re-starting the infusion, and prior to the next scheduled dose of IMCnyeso ○ The restarted infusion rate does not exceed 50% of previous rate ○ Vital signs are monitored at least approximately every 15 minutes until the infusion is completed • If Grade 2 IRR resolves > 4 hours after onset, or if Grade 2 IRR recurs after re-starting the infusion at a reduced rate and despite oral pre-medication, do not resume infusion. Treatment may continue at the next scheduled dose. Consider oral pre-medications for subsequent IMCnyeso doses (eg, 1000 mg of acetaminophen [paracetamol] and 50–100 mg diphenhydramine hydrochloride or alternative antihistamine within 60 minutes prior to the start of infusion).

Grade	Recommended Toxicity Management	Dose Modifications
Grade 3	As above for Grade 2; additionally, consider systemic immunosuppressive agents (eg, methylprednisolone 1 mg/kg IV twice daily) and high-dose or multiple vasoressors as clinically indicated per institutional standards.	
Discontinue infusion immediately.
 
 • If a Grade 3 IRR improves to \leq Grade 1 within 6 hours of onset with medical management, treatment may continue with the next scheduled dose of IMCnyeso; if resolution requires $>$ 6 hours, treatment may continue with a ≥ 1 dose-level reduction • The next scheduled dose is to be delivered using a rate of infusion not to exceed 50% of rate used when the IRR occurred • Oral pre-medications (eg, 1000 mg of acetaminophen [paracetamol], 50–100 mg diphenhydramine hydrochloride or alternative antihistamine) are to be given within 60 minutes prior to the next scheduled dose of IMCnyeso • If Grade 3 IRR recurs after re-starting IMCnyeso treatment, dosing should be permanently discontinued unless the Investigator believes the overall benefit-risk favors continued treatment and following discussion and agreement with the Sponsor Medical Monitor
Grade 4	Treat as above for Grade 3 infusion-related reaction.	Permanently discontinue study treatment
Hepatic Function Abnormalities		
Grade 2	Regular monitoring of liver function tests until improving or resolved. Evaluate concurrent medications for agents that may prolong or exacerbate laboratory abnormalities. Consider IV corticosteroid therapy (eg, hydrocortisone 100 mg or the equivalent) if not improving within 72 hours.	May continue dosing.

Grade	Recommended Toxicity Management	Dose Modifications
Grade 3	
Notify the Sponsor within 24 hours.
 
As above for Grade 2; additionally, consider further testing to assess liver synthetic function and consider hepatology consult to advise on management and additional workup. Consider IV corticosteroid therapy (eg, hydrocortisone 100 mg or equivalent) per institutional guidelines if not resolving within 48 to 72 hours.
	
Do not administer IMCnyeso until LFTs have improved to \leq Grade 1 and following discussion and agreement with the Sponsor Medical Monitor.
 
 For isolated ALT and/or AST elevation ($>5-8 \times$ ULN) or isolated total bilirubin elevation ($>3-5 \times$ ULN) that resolves to Grade ≤ 1 within 7 days, dosing at the current dose level may resume For isolated ALT and/or AST elevation ($>5-8 \times$ ULN) or isolated total bilirubin elevation ($>3-5 \times$ ULN) that requires > 7 days to resolve, dosing may resume with ≥ 1 dose-level reduction in IMCnyeso For isolated ALT and/or AST elevation ($>8 \times$ ULN) or isolated total bilirubin elevation ($>5 \times$ ULN) that resolves to Grade ≤ 1, dosing should be permanently discontinued unless the Investigator believes the overall benefit-risk favors continued treatment, in which case dosing may resume with ≥ 1 dose-level reduction in IMCnyeso
Grade 4	
As above for Grade 3; additionally, promptly consider IV corticosteroid therapy (eg, hydrocortisone 100 mg or equivalent) per institutional guidelines if not resolving within 24 hours. Perform supplementary testing to assess liver synthetic function and obtain hepatology consult to advise on management and additional workup.
	
Study medication must be permanently discontinued.

Grade	Recommended Toxicity Management	Dose Modifications
Vomiting		
Grade 2	Anti-emetic therapy as per institutional standard. IV fluids, electrolyte supplementation, and other supportive measures for additional adverse events as needed.	May continue dosing.
Grade 3	Anti-emetic therapy as per institutional standard. IV fluid support and other supportive measures for additional adverse events.	
If Grade 3 vomiting persists > 3 days, do not administer IMCnyeso until vomiting has improved to \leq Grade 1.
 
 • If Grade 3 vomiting resolves to \leq Grade 1 within 3 days of onset, dosing at the current dose level may continue at the next scheduled dose • If Grade 3 vomiting requires > 3 days to resolve to \leq Grade 1, a ≥ 1 dose-level reduction is required for the next scheduled dose of IMCnyeso
Grade 4	As above for Grade 3.	
Do not administer IMCnyeso until vomiting has improved to \leq Grade 1.
 
A ≥ 1 dose-level reduction is required for the next scheduled dose of IMCnyeso

Other Adverse Events		
Grade 1 or 2	Manage according to institutional practice. Monitor as clinically indicated for potential worsening and assess whether more intense medical intervention is indicated.	May continue dosing.
Grade 3 or 4	Treat according to institutional practice. For immune-related AE, consider treatment with corticosteroids. Consult Sponsor Medical Monitor for further guidance as needed.	Consider not administering IMCnyeso until toxicity has improved to \leq Grade 1.

COPD = chronic obstructive pulmonary disease; CRS = cytokine release syndrome; CTCAE = Common Terminology Criteria for Adverse Events; IRR = infusion-related reaction; IV = intravenous; LFT = liver function test; NCI = National Cancer Institute.

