6.10 Dose-Escalation Decision Making

Dosing will begin with the first cohort at the starting dose of 3 mcg QW (Table 6-2). All doses administered to subsequent cohorts of patients will be determined by the SST and will be guided by the BLRM and will be subject to both the EWOC principle and the escalation rule.

Dose-escalation decisions will be made by the SST, which will consist of the Study Investigators, the Sponsor Medical Monitor, and a statistician. For each cohort, dose escalation or de-escalation decisions will be based on the SST's review of all relevant data available, from all dose levels evaluated in the ongoing study, including safety information, DLTs, all \geq Grade 2 toxicity data, PK, and pharmacodynamic data from evaluable patients (as defined in Section 6.10.2). The data and BLRM dose recommendations will be discussed and agreed upon during the dose-escalation teleconference (DETC), and all decisions will be documented in the meeting minutes and shared with all participating Principal Investigators.

If toxicity resolves following appropriate management and provided treatment discontinuation criteria are not met (see Section 6.16), patients experiencing DLTs may continue treatment with IMCnyeso only after agreement with the Sponsor Medical Monitor. With each dose cohort in Phase I, determination of the next dose to be tested in the dose escalation will be guided by the BLRM. Decision making will be based on all evaluable patients in the dose-determining set (DDS) at each cohort level (see Section 6.10.1). At each decision point, the BLRM provides an estimate of all dose levels of IMCnyeso that do not exceed the MTD and incorporates all DLT information at all dose levels for this estimation (see Section 9). In general, the next dose will have the highest chance that the true DLT rate will fall in the target interval (16%–33%) and will always satisfy the EWOC principle. In all cases, the dose for the next cohort will not exceed a 3.34-fold increase from the previous dose. Smaller dose increases may be recommended by the

Investigators and Sponsor upon consideration of all available clinical data. Further details of the BLRM including additional simulated escalation pathways are provided in [Section 13.3](#).

The estimated dose levels to be tested in this study (in the scenario that no DLT are reported) are shown in [Table 6-2](#). Actual doses will be determined using the BLRM and must be agreed upon by the SST.

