6.12 Definitions of Dose-Limiting Toxicity

A DLT is defined as an AE or abnormal laboratory value assessed as having a suspected relationship to study drug that occurs within the DLT evaluation period (Section 6.10.2), is unrelated to disease, disease progression, inter-current illness, or concomitant medications, and meets any of the criteria included in Table 6-3. Any death not clearly due to the underlying disease or extraneous causes will be considered a DLT. Other clinically significant toxicities, including a single event or multiple occurrences of the same event that lead to a dosing delay or interruption lasting > 7 days in Cycle 1, may be considered a DLT by the SST, even if not \geq Grade 3. Events meeting DLT criteria but occurring outside the DLT evaluation period may also be considered DLT by the SST. In the absence of clinically significant signs or symptoms, abnormal laboratory values that potentially meet DLT criteria must be confirmed by re-testing at least 24 hours after the initial observation.

Cytokine release syndrome will be graded based on the ASTCT 2019 criteria in [Section 13.1](#). NCI CTCAE version 4.03 will be used for all other grading. The Investigator must notify the Sponsor within 24 hours of any DLT (additional events requiring reporting within 24 hours are listed in [Section 8.5](#)).

Guidance for toxicity management is in [Section 6.15](#).

Table 6-3: Criteria for Defining Dose-Limiting Toxicities

DLTs include \geq Grade 3 AE occurring during the DLT evaluation period, with a suspected relationship to study drug, with the following modifications:	
Hematology	Grade 4 neutropenia persisting > 5 days after onset or associated with infection is a DLT \geq Grade 3 febrile neutropenia is a DLT Grade 4 thrombocytopenia or \geq Grade 3 thrombocytopenia associated with \geq Grade 3 bleeding is a DLT Grade 4 anemia is a DLT \geq Grade 3 lymphopenia in the presence of an infection indicating clinical significance is a DLT

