Hepatic and pancreatic	Grade ≥ 2 elevated total bilirubin ($> 2 \times$ ULN) with concurrent Grade ≥ 2 elevated ALT and/or AST ($> 3 \times$ ULN), with no clear alternate etiology (eg, biliary obstruction with elevated alkaline phosphatase), is a DLT Grade 3 isolated ALT and/or AST ($> 5-8 \times$ ULN) elevation or Grade 3 isolated bilirubin elevation ($> 3-5 \times$ ULN) that does not resolve to \leq Grade 1 within 14 days of onset is a DLT \geq Grade 3 isolated ALT and/or AST ($> 8 \times$ ULN) elevation or \geq Grade 3 isolated bilirubin ($> 5 \times$ ULN) elevation is a DLT \geq Grade 3 amylase and/or lipase elevation, with associated clinical signs, symptoms, or radiographic evidence of pancreatitis, is a DLT
Gastrointestinal	Grade 3 nausea, vomiting or diarrhea persisting for > 3 days after onset, despite optimal therapy, is a DLT
Hypotension	Grade 3 hypotension that does not resolve to \leq Grade 1 within 6 hours of onset, despite optimal therapy, is a DLT Grade 4 hypotension of any duration and with any management is a DLT
Hypertension	Grade 3 hypertension (systolic BP ≥ 160 mm Hg or diastolic BP ≥ 100 mm Hg) persisting > 2 days after onset, despite treatment, is a DLT Grade 4 hypertension of any duration is a DLT
Infection	Grade 3 infection or fever in the absence of neutropenia that persists > 7 days after onset is a DLT Grade 4 infection of any duration is a DLT

DLTs include \geq Grade 3 AE occurring during the DLT evaluation period, with a suspected relationship to study drug, with the following modifications:	
Tumor Flare	Grade 3 inflammatory reaction at a tumor site associated with local anti-tumor immune response that does not resolve to \leq Grade 2 within 7 days after onset is a DLT
Electrolyte Abnormalities	Grade 3 electrolyte abnormalities that do not resolve to \leq Grade 1 within 3 days after onset, despite optimal medical management, are DLTs Grade 4 electrolyte abnormality of any duration is a DLT
Skin toxicity	Grade 3 rash and/or pruritis that persists $>$ 7 days after onset, despite optimal medical management, is a DLT Grade 4 cutaneous toxicity of any duration is a DLT
Fatigue	\geq Grade 3 fatigue that persists $>$ 4 days after onset is a DLT
Infusion-related reaction / hypersensitivity / anaphylaxis	Grade 3 infusion-related reaction that does not resolve to \leq Grade 1 within 6 hours of onset, despite appropriate medical management, is a DLT Grade 4 infusion reaction is a DLT

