6.16 Treatment Discontinuation

Reasons for discontinuation of study treatment will include:

- Disease progression (Note: Patients may receive treatment after initial disease progression per RECIST v1.1 based on criteria in [Section 6.18](#))
- Initiation of alternative anti-cancer therapy including another investigational agent
- Unacceptable toxicity as defined in [Table 6-3](#) or any AE that, in the opinion of the Investigator or the Sponsor, contraindicates further dosing
- Withdrawal of consent for further treatment
- Lost to follow-up
- Patient is determined to have met 1 or more of the exclusion criteria or failed to meet all inclusion criteria AND continuing to receive IMCnyeso might constitute a safety risk. Patients who fall into this category and for whom continuation of treatment is not thought by the Investigator to pose a safety risk may, after discussion with the Sponsor Medical Monitor, continue to receive study treatment
- Pregnancy or intent to become pregnant

Information about the EOT visit and follow-up periods is provided in [Section 7.3](#).

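### Table 6-4 permits dosing, with no Sponsor notice, during a combined Grade 2 bilirubin and transaminase rise that Table 6-3 makes a DLT; after Day 28 no explicit rule overrides that permission

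*Protocol*

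**What the plan says.** **DLT definition.** Under the hepatic criteria of Table 6-3 (protocol Section 6.12), total bilirubin above 2 x ULN with concurrent ALT and/or AST above 3 x ULN "with no clear alternate etiology (eg, biliary obstruction with elevated alkaline phosphatase), is a DLT". No minimum duration is set. Section 6.12 adds that the event must be suspected to be drug-related and fall in the evaluation period (28 days, Section 6.10.2). If there are no clinically significant signs or symptoms, it must also be confirmed by a retest at least 24 hours later. For management, Section 6.12 sends the site to Section 6.15. For late events it says: "Events meeting DLT criteria but occurring outside the DLT evaluation period may also be considered DLT by the SST".

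**Toxicity table.** The hepatic Grade 2 row of Table 6-4 (Section 6.15.2) asks for "Regular monitoring of liver function tests until improving or resolved", a review of other medicines, and consideration of IV steroids "if not improving within 72 hours". Its dosing cell lets treatment go on, and it has no Sponsor-notification line. The Grade 3 row requires 24-hour notice and a hold: "Do not administer IMCnyeso until LFTs have improved to" Grade 1 or lower, with Medical Monitor agreement. All three of its restart bullets are limited to isolated elevations.

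**Other dosing rules.** Section 6.10 says that, once toxicity has resolved and if no Section 6.16 criterion is met, "patients experiencing DLTs may continue treatment with IMCnyeso only after agreement with the Sponsor Medical Monitor". Section 6.16 lists as reasons to stop treatment "Unacceptable toxicity as defined in" Table 6-3 "or any AE that, in the opinion of the Investigator or the Sponsor, contraindicates further dosing".

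**24-hour notice.** Section 8.5 and the Synopsis list SAEs, DLTs, CRS of Grade 2 or higher, and hepatic abnormalities of Grade 3 or higher.

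**The concern.** Dosing is weekly, and Table 6-4 is where a site looks when liver tests rise. Read alone, it permits the next dose during a combined bilirubin and transaminase signal. The Global Amendment 2 summary says that the sponsor aligned this DLT criterion with potential Hy's Law, so this is a signal the sponsor chose to treat as dose-limiting on sight. What is at stake is patient safety: re-dosing during a possible drug-induced liver injury, and late awareness at the Sponsor.

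The period after Day 28 carries real exposure:
- Under Section 6.10.1, a patient may move to a higher dose after at least 3 cycles, so exposure to a new dose can begin outside the DLT window.
- From Cycle 4, Table 7-2 schedules chemistry on Day 1 only of each 28-day cycle, against doses on Days 1, 8, 15 and 22. That is one scheduled panel per four doses.
- The Phase II safety review trigger in Section 6.11 counts only Grade 3 and 4 events, so a Grade 2 plus Grade 2 event would not count towards it.

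**Working it through.** The plan gives no figure to reproduce. The check is a comparison of rules.

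**1. The affected band.** Lower bounds come from Table 6-3: bilirubin > 2 x ULN, ALT/AST > 3 x ULN. Upper bounds are where Grade 3 begins in Tables 6-3 and 6-4: bilirubin > 3 x ULN, ALT/AST > 5 x ULN. The band is therefore bilirubin > 2 to 3 x ULN together with ALT and/or AST > 3 to 5 x ULN. If either value reaches Grade 3, the opening hold and notice of the Grade 3 row apply, and the event is outside this point.

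**2. What each rule says about an event in the band** (drug-related, no other clear cause, confirmed where required):

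| Provision | Days 1-28 | After Day 28 |
|---|---|---|
| Section 6.12, Table 6-3 | DLT | DLT only if the SST chooses |
| Table 6-4, hepatic Grade 2 | Dosing permitted, no notice | Same |
| Section 6.10 | Resolution, Section 6.16 not met, Medical Monitor agreement | Applies only if called a DLT |
| Section 6.16, Table 6-3 limb | Reason to stop | Unclear (step 3) |
| Section 6.16, opinion limb | Discretionary | Discretionary |
| Section 6.15.2, omission of one or two doses | Optional | Optional |
| Section 8.5, 24-hour notice | Required, as a DLT | Only if judged an SAE or called a DLT |

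**3. Reach of Section 6.16 after Day 28.** The section is not limited by cycle or phase, which suggests that it borrows the Table 6-3 thresholds at any time. But the heading of Table 6-3 confines its contents to the DLT evaluation period. Both readings are open, and neither produces a 24-hour notice.

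**4. The 72-hour prompt.** It implies a reassessment before the following weekly dose (3 days against at least 7). The dosing cell does not change with the result.

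**5. Ordering against neighbouring rows.**
- Isolated ALT/AST > 5 to 8 x ULN that settles to Grade 1 or lower within 14 days is not a DLT. It still gets a hold, Medical Monitor agreement and 24-hour notice.
- Grade 2 CRS is not among the listed CRS DLTs. It still gets a hold until resolution and 24-hour notice.
- The combined hepatic event is a DLT at once, yet its row gives neither. The table can set a hold at Grade 2, so this looks like an omission.

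**6. Can a hold be released?** The ALT/AST entry limit is 3 x ULN (Section 5.3), equal to the > 3 x ULN cut-off, so no eligible patient starts above it. The bilirubin limit is 1.5 x ULN, but 3.0 x ULN in Gilbert's syndrome. Such a patient may start up to 3.0 - 2.0 = 1.0 x ULN above the trigger, so the new rule needs a baseline provision.

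**The case against.** **A reader might infer that Table 6-4 flatly contradicts Sections 6.10 and 6.16 in Days 1-28, or that a Cycle 1 DLT could go unreported.** The documents do not support this. Table 6-4 is titled as recommended management, and its Grade 2 cell grants a permission rather than ordering a dose. Sections 6.10 and 6.16 narrow that permission, so all three can be followed together. The 24-hour notice is mandatory because the event is a DLT.

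**A reader might also infer that patients are unprotected after Day 28.** That too goes further than the text. SST designation, SAE reporting as medically significant, optional dose omission, the opinion limb of Section 6.16 and the 72-hour prompt all remain. Each depends on judgement or, like the prompt, does not govern dosing.

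**Table 6-4 does not mirror Table 6-3 in general.** Grade 3 febrile neutropenia, or Grade 3 fatigue beyond 4 days, is a DLT but falls under the row for other adverse events, which only suggests considering a hold. This is fair as a description of the table's structure. But that row at least raises withholding, whereas the hepatic Grade 2 row gives permission without qualification.

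**The broad reading of Section 6.16 is the natural one.** Treatment is open-ended, and a limb that lapsed at Day 28 would do nothing for most of it. This is the strongest reply and stands in part: on that reading, dosing is addressed at any time. The Table 6-3 heading still allows the narrower reading, and the notice gap remains on either.

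**Judgement over Grade 2 laboratory values is a legitimate choice, and the risk is low.** Section 13.5.2 justifies less later testing by a lower risk of new related events. Section 1.4 reports no DLT and no treatment-related event of Grade 3 or higher in 15 patients. But those data stop at 100 mcg, while SAP Table 1 lists 180 and 300 mcg cohorts. The sponsor has also already removed discretion over this combination within the DLT window.

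**Conclusion.** The point holds in two parts of unequal weight. In Days 1-28 the fault is small: an unqualified permission in the table that sites are sent to, with dosing and notice already controlled elsewhere. The exposure is a site that relies on Table 6-4 alone. After Day 28, in both phases, the gap is real. No explicit hold or 24-hour notice covers the event, and the remaining routes are discretionary or depend on how Section 6.16 is read.

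The size is the band itself: bilirubin > 2 to 3 x ULN with ALT and/or AST > 3 to 5 x ULN, drug-related and with no other clear cause. Frequency cannot be derived from the documents, although Section 1.4 names raised transaminases and bilirubin as possible effects.

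This rests on two assumptions. Cycle 1 of Phase II is treated as inside the DLT window, because SAP Sections 4 and 8.1 provide for DLT reporting in Phase II; if it is not, the gap there starts at Day 1. Section 6.10 is a dose-escalation section, so its restriction is clearest in Phase I. The point merits an amendment because a written rule permits re-dosing during a signal that the sponsor itself classes as dose-limiting.

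**What to change.** Add a row to Table 6-4, for all cycles and both phases, for concurrent total bilirubin > 2 x ULN and ALT and/or AST > 3 x ULN with no other clear cause. Gilbert's syndrome with bilirubin at its baseline level should count as another cause for the bilirubin component. The row should say:
- Hold IMCnyeso until liver tests are Grade 1 or lower, or bilirubin is back to baseline in Gilbert's syndrome.
- Permanently discontinue unless the Investigator judges that benefit-risk favors continuing and the Sponsor Medical Monitor agrees.
- Notify the Sponsor within 24 hours.
- Where either value is Grade 3 or 4, the stricter row applies.

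The row needs its own restart rule. If it deferred to Section 6.16, it would import that section's uncertainty; on the broad reading, a restart could never occur. State in Section 6.16 that this row governs the event at any time on treatment. Add the event to the 24-hour list in Section 8.5 and the Synopsis.

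The cost is one table row, one sentence and one repeated clause in an amendment. In use, expect occasional missed doses or discontinuations and a few more notices. A hold beyond 21 days would also meet the existing default of permanent discontinuation in Section 6.15.2.
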